2.2 OVERVIEW

TRC-PAD is an ambitious program, addressing wide-ranging issues in trial recruitment and site management. To succeed, it will build on existing efforts by expert collaborators in informatics, web-based consent, innovative cognitive assessments, biostatistics, and multiple existing registry programs.

The feeder registries (Brain Health Registry, Alzheimer's Prevention Registry, HealthyBrains.org, et al.) will filter participants based on age and cognitive status and invite older individuals not meeting criteria for dementia to enroll in the APT Webstudy, which in turn will conduct unsupervised, web-based capture of demographic, medical, lifestyle and genetic factors, as well as longitudinal web-based cognitive testing and symptom questionnaires, to assess their risk of elevated brain amyloid. The initial risk algorithm is derived from analysis of an existing study data. This algorithm is then iteratively updated through an appropriate regression-based statistical approach to biomarker testing results.

The individuals at highest risk within the APT Webstudy pool of asymptomatic (preclinical) and very mildly symptomatic (prodromal) individuals will be referred for in-person clinical and biomarker assessments at select AD clinical trial sites. Those who are identified with biomarker profiles indicative of AD pathology, including asymptomatic individuals with minimally elevated or "intermediate" levels of amyloid, will be eligible for the in-clinic trial-ready cohort (TRC), where they will be followed at semi-annual in person visits until they are ready for enrollment in preclinical/prodromal therapeutic trials, while continuing quarterly, remote, web-based cognitive assessments in the APT Webstudy. Biomarker-negative individuals will continue remote web-based follow-up in the APT Webstudy; if longitudinal trajectories and changes to other risk factors indicate increasing risk, those participants will be eligible for repeat in-person clinical and biomarker assessment. Participants with known

biomarker status may have direct referral to the in-clinic TRC cohort and will be encouraged to participate in the APT Webstudy.

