2.3.1.4 PSYCHOLOGICAL RISKS OF REFERRAL FROM THE APT WEBSTUDY

When a participant is identified as having increased risk for future development of AD based on their profile and performance in the APT Webstudy, they will be contacted by email or phone to present for an in-clinic evaluation to have their increased risk explained and to consent for screening to join the in-clinic TRC-PAD cohort. Participants deemed ineligible at the in-clinic evaluation may be referred for further clinical evaluation of a non-AD diagnosis and/or returned to the APT Webstudy for continued tracking. Risks associated with this process include negative outlook based on the invitation for further evaluation of memory performance as part of the APT Webstudy. In the case of individuals referred from other studies where their amyloid status may be known, they might be referred to in-clinic evaluation to join the TRC-PAD cohort if eligible. These individuals may therefore bypass the APT Webstudy completely.

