8 STUDY ASSESSMENTS AND PROCEDURES

8.1 CLINICAL AND COGNITIVE ASSESSMENTS

8.1.1 PRESCREEN PHASE

During the prescreen phase, participants will be enrolled in the APT Webstudy and once triggered for increased risk of developing AD, will be referred to in-person clinical evaluation. Participants for whom evidence of brain amyloid has already been confirmed, may be referred for in-person clinical evaluation to participate in TRC and bypass the APT Webstudy.

Prior amyloid testing, when applicable, should be confirmed prior to screening.

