Analysis Plan: Initial amyloid PET results will be compared to historical data from preclinical and prodromal studies for which similar data can be obtained and, for prodromal participants, published data from gantenerumab and avagacestat studies. Standard statistical methods (t-tests for continuous measures and chi-square tests for categorical measures) will be used to compare the participants identified as biomarker positive and biomarker negative. Associations between an indicator of biomarker positivity and each of the potential risk factors will be assessed in a two-staged manner using a generalized linear model with a logit-link function or a generalized linear mixed model for binary data (to account for the measurements over time for an individual participant). Univariate associations deemed to be statistically significant ($p < 0.15$) will be included in a multivariable logistic regression model. Potential confounding and effect-modifying variables will be included in the model as covariates, if necessary. The risk factors and the appropriate functional form of these factors that will be utilized in the model will be clearly stated in the SAP and will be based on the results of the preliminary analysis. An individual participant's predicted risk of biomarker positivity will be calculated using the final multivariable risk prediction model and serve as a risk-algorithm. The performance of this model will be assessed using four measures: the concordance index (c-index) to evaluate the discrimination ability, the calibration slope and calibration in the large to evaluate the model calibration, and decision-curve analysis to assess clinical usefulness. The model will be internally validated using 10-fold cross-validation and bootstrap sampling.

Power Analysis: Power analysis was done using a comparison of the area under a ROC curve (AUC) with a null hypothesis value of 0.75. Assuming a total sample size of 2000 participants and a 60% amyloid expected positivity rate, we have 90% power to detect an AUC of at least 0.80 using a two-sided z-test and a level of significance of 5%.

Statistical Aim 3: Baseline and longitudinal cognitive performance, (including lack of practice effect on repeated web-based cognitive tests), decline on performance based functional measures, and a combination of self- and study-partner report will predict and subsequently track with in-person measures of cognitive (PACC) and functional (CDR-SB) decline.

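### Aim 2 screens risk factors by univariate p < 0.15 in people referred on a joint risk score, so weaker true predictors in that score can drop out of the final algorithm

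*Combined protocol and SAP*

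**What the plan says.** The Aim 2 analysis plan in section 9 builds the risk model in two stages. The first stage is a screen: "Univariate associations deemed to be statistically significant ($p < 0.15$) will be included in a multivariable logistic regression model". The final multivariable model supplies each participant's predicted risk and becomes the risk algorithm.

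Two sentences qualify the screen. One reads "Potential confounding and effect-modifying variables will be included in the model as covariates, if necessary". The other reads "The risk factors and the appropriate functional form of these factors that will be utilized in the model will be clearly stated in the SAP"; it bases that list on the preliminary analysis. The opening of section 9 describes that analysis as a mid-study look for sources of bias, confounding among them. Validation is by cross-validation and bootstrap, both within the tested sample.

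On who is tested, section 2.2 points to "The individuals at highest risk within the APT Webstudy pool", and section 8.1.1 says Webstudy participants, "once triggered for increased risk of developing AD, will be referred to in-person clinical evaluation". Section 2.2 also says of the referral algorithm: "This algorithm is then iteratively updated through an appropriate regression-based statistical approach to biomarker testing results". People with known amyloid status form a second route, and section 2.3.1.4 says of them: "These individuals may therefore bypass the APT Webstudy completely".

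**The concern.** The question for each factor is whether it predicts amyloid positivity given the others. The screen asks something else: whether the factor, taken alone, is associated with positivity among those tested. The two answers diverge when people were tested because a sum of these factors was high. A referred person with a low age contribution must have reached the threshold through something else, such as genotype or cognition. Within the referred group the inputs offset one another, and each unadjusted association moves towards zero although the adjusted effect is unchanged.

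A model holding all the score's inputs does not have this problem, but under the plan it receives only what passes the screen. At stake is the final Aim 2 model, which is meant to reduce biomarker screen failures when applied to a broad pool. Validation inside the tested sample would not show the loss in that pool.

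**Working it through.** **The plan's own figure.** Aim 2 gives one calculation: 90% power for AUC 0.80 against 0.75 with 2,000 participants, 60% positive, two-sided 5%. By Hanley-McNeil, Var(A) = [A(1−A) + (n1−1)(A/(2−A) − A²) + (n0−1)(2A²/(1+A) − A²)]/(n1·n0), with n1 = 1,200 and n0 = 800. This gives SE = 0.01067 at 0.75 and 0.00963 at 0.80. Power = Φ[(0.05 − 1.96 × 0.01067)/0.00963] = Φ(3.02) = 99.9%; a binormal variance gives 99.4%. The stated 90% is conservative, and nothing below depends on it.

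**Mechanism.** Let logit P(Y=1|X) = α + Σβ_jX_j, and let people be tested when Σw_jX_j ≥ c. Testing depends only on X, so P(Y|X, tested) = P(Y|X), and the model with all inputs still estimates the β_j. The unadjusted slope for factor j is roughly β_j + Σ_{k≠j} β_kδ_kj, where δ_kj is the slope of X_k on X_j among those tested. Selection on the sum makes the δ_kj negative.

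**Inputs.** From the documents: the p < 0.15 rule, referral of the highest-risk people, and N = 2,000. Assumed, because the documents name only broad groups of factors: four independent predictors with log-odds 0.6 (age, per SD), 1.0 (APOE4, per allele), 0.4 (cognition, per SD) and 0.3 (family history); 30% positive in the pool; and the fraction tested. Where needed, APOE4 allele frequency was set at 0.2 and family history at 40%.

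**Results, 2,000 tested.** Ranges are across repeated simulations of 100 to 300 replicates.

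| | Unselected | Top 50% | Top 25% | Top 10% |
|---|---|---|---|---|
| Age passes the screen | 100% | 100% | 92–96% | 67–78% |
| APOE4 passes | 100% | 100% | 100% | 91–95% |
| Cognition passes | 100% | 92% | 65–72% | 37–43% |
| Family history passes | 89% | 38% | 23–27% | 16–27% |
| At least one dropped | 11% | 66–74% | 83–88% | 96–98% |
| Pool AUC loss against full model | about 0 | 0.003–0.004 | 0.011–0.014 | 0.035–0.04 |

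In the same selected samples, each factor meets p < 0.15 in the full model 92–100% of the time. At top 25%, the age–APOE4 correlation is about −0.47. The mean unadjusted coefficient for age is about 0.16, against an adjusted 0.60; for family history it is 0.06 against 0.30.

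Setting positivity at the plan's 60% among those tested, at least one predictor is lost in 86% (top 25%) and 97% (top 10%) of runs. The AUC losses are 0.729 − 0.715 = 0.014 and 0.734 − 0.704 = 0.030.

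**A second assumed set.** Five predictors: log-odds 1.3 (binary, 30% prevalence); 0.5, 0.3 and 0.15 per SD; and 0.25 (binary, 50% prevalence), with 60% positive among those tested. At least one is dropped in 24% of unselected samples and in 94%, 98% and 99% at top 50%, 20% and 10%. The AUC losses are 0.715 − 0.704 = 0.011, 0.719 − 0.687 = 0.032 and 0.717 − 0.653 = 0.064. The strong binary factor passes 100%, 70% and 30% of the time, so tight selection can remove even a dominant input. When the 0.15-per-SD factor is left out of the referral score, it passes about 95% of the time.

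**What shrinks or enlarges the effect.**
- Referral that follows the score loosely (correlation about 0.7): only the weakest factor suffers, falling from 89% to 53%.
- A quarter of those tested unselected: almost no AUC loss, though some predictor still drops in 19–37% of runs.
- 2,000/0.60 = 3,333 tested: the loss is 0.006–0.009 at top 25% and 0.017–0.020 at top 10%. In the second set it is still 0.717 − 0.665 = 0.052 at top 10%.
- A misweighted referral score at top 25%: age passes only 18% of the time and pool AUC is 0.67.

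**The case against.** **The plan has other routes into the model.** The covariate clause, the deferred factor list and the mid-study bias review could each rescue a lost predictor. This stands as mitigation. But all three are discretionary, none requires score inputs to be kept, and the list itself rests on a preliminary analysis with no stated correction for referral.

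**The inputs are assumed.** This is true, and it limits the size. Section 1.2 makes remote APOE genotyping optional, so APOE may lie outside the referral score. In that case APOE4 always passes, age passes 95–100% of the time, and the AUC loss is 0.723 − 0.713 = 0.010 (top 25%) or 0.723 − 0.705 = 0.018 (top 10%). If genotype is available for half the pool, the loss is not reduced: 0.724 − 0.710 = 0.014 and 0.724 − 0.673 = 0.051.

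**More than 2,000 may be tested.** The enrolment goal of 2,000 counts people who meet the amyloid criterion, while the Aim 2 power statement uses 2,000 at 60% positive. The intended number is unclear, and a larger one softens the effect.

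**Direct referrals dilute the selection.** A truly unselected group would, but the documents describe none. Direct referrals come with amyloid already confirmed, so they are selected on the outcome and may have no Webstudy predictor data.

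**Two stronger readings lack support.** A reader might infer that the in-study updates of the referral algorithm also use the screen. Section 2.2 asks only for a suitable regression approach, the p < 0.15 rule appears only under Aim 2, and section 9 places the analyses at the end of the grant cycle. A reader might also infer that dropped factors would be published as unrelated to amyloid. Nothing says so, and section 9 commits to estimates with confidence intervals.

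**Conclusion.** The concern holds for the final Aim 2 model. Followed as written, the screen can remove weaker true predictors that are already in the referral score, and under both assumed sets at least one is usually lost when half or less of the pool is tested. Strong factors mostly survive, except under tight selection, and factors outside the score mostly survive throughout.

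The practical loss is modest unless selection is tight. With four assumed predictors and 2,000 tested, pool AUC falls by about 0.003, 0.014 and 0.04 at top 50%, 25% and 10%. These figures rest on assumed effects, independent predictors in the pool and referral that follows the score closely. It would go too far to say that true predictors certainly will be dropped: the documents do not give the cut-off, weights or factor list that would settle it. The change is still worth making, because it uses the same data and the existing safeguards do not require the right variables to be kept.

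**What to change.** In section 9 and the SAP, delete the univariate p < 0.15 entry rule. Enter every input of the referral score, together with the prespecified new candidates, in one multivariable logistic model, preferably penalised (ridge or lasso). Do not drop a score input on its unadjusted p-value. Because the score is updated during the study, list the inputs of each version used for referral. Keep the univariate results as a descriptive table, labelled as describing the referred group only.

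The cost is a wording change and no new data. A few more coefficients are estimated, with slightly wider intervals because the inputs are correlated after selection.

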6 PET TRACERS

Each participant receiving a PET scan for eligibility confirmation will be scanned with an Amyloid PET tracer – which tracer is used will be determined based on availability at the site for this study. Amyloid PET results will be generated centrally using quantitative metrics to assess level of amyloidosis, and eligibility information for continuing in the TRC cohort will be returned to site.

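### Under the planned internal validation, calibration-in-the-large of the Aim 2 risk model is about 0 whatever the model's quality, so it cannot show miscalibration at other sites or in later recruitment

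*Combined protocol and SAP*

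**What the plan says.** The Aim 2 analysis plan in Section 9 relates biomarker positivity to each risk factor "using a generalized linear model with a logit-link function or a generalized linear mixed model for binary data". Factors that pass a univariate screen at p < 0.15 "will be included in a multivariable logistic regression model", and the predicted risks from that model serve as the algorithm. Then: "The performance of this model will be assessed using four measures". These are the c-index, two calibration measures ("the calibration slope and calibration in the large to evaluate the model calibration") and decision-curve analysis. On validation the text says: "The model will be internally validated using 10-fold cross-validation and bootstrap sampling". It does not state the unit of the folds or resamples, and it sets no acceptance limit for either calibration measure. I found no temporal, site-held-out or external check of the model in the combined protocol and SAP.

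The setting is varied. Section 1.1 foresees about 60 sites. Under Section 6, "which tracer is used will be determined based on availability at the site for this study". Amyloid status may come from PET, CSF or earlier external testing (Sections 1.3 and 8.1.2.1). Section 2.2 describes an algorithm that starts from existing data and is updated repeatedly as biomarker results arrive.

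**The concern.** Calibration-in-the-large asks whether average predicted risk matches the observed positivity rate. It is useful only where the two can differ. Here the model's intercept is estimated from the same people on whom the measure is then computed, or from random subsets with the same positivity rate. Agreement is close to automatic.

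Aim 2 promises fewer biomarker screen failures in future trials, which is a statement about people not yet tested. The error that would damage it is a baseline positivity at some sites, or in a later recruitment period, that differs from what the model predicts. Random resampling mixes sites and periods together and averages such differences out. Decision-curve analysis also rests on absolute risk and, computed internally, has the same blind spot. A reported value near 0 could then be read as evidence of good calibration when it says almost nothing.

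**Working it through.** The plan gives no value or limit for calibration-in-the-large, so there is no figure to reproduce.

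**Inputs from Section 9, Aim 2.** "Assuming a total sample size of 2000 participants and a 60% amyloid expected positivity rate"; multivariable logistic model; univariate screen at p < 0.15; 10-fold cross-validation and bootstrap; null AUC 0.75.

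**Assumptions.** Maximum likelihood with an intercept; ordinary random folds and resamples; 20 candidate predictors; in the useful model, six of them with log-odds 0.5 each.

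**Step 1, fitted data.** Calibration-in-the-large is the value a in logit P(y = 1) = a + lp, with the linear predictor lp as an offset. It solves sum(y - expit(a + lp)) = 0. The likelihood equation for the model's own intercept is sum(y - p) = 0, so a = 0 exactly for any set of predictors.

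**Step 2, 10-fold cross-validation.** Take an intercept-only model and ten equal folds with positive rates r_j and overall rate r. Fold j is predicted at (10r - r_j)/9. The average prediction over folds is (10r - r)/9 = r, so a = 0 again. With predictors the result is no longer exact, but only small estimation noise is added.

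**Step 3, bootstrap.** The positivity rate of one resample varies around the sample's own rate with a logit-scale SD of about 1/sqrt(2000 × 0.6 × 0.4) = 1/sqrt(480) = 0.046. Averaged over 30 resamples this is 0.046/sqrt(30) = 0.008. More resamples make it smaller.

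**Step 4, simulation.** N = 2,000, 60% positive, screen repeated inside every fold and resample, 30 bootstrap resamples, 60 replicates. CITL stands for calibration-in-the-large.

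| Quantity | Useless model | Useful model |
|---|---|---|
| Apparent CITL | 0 | 0 |
| Cross-validated CITL, mean (SD; largest absolute value) | 0.000 (0.002; 0.006) | -0.0005 (0.002; 0.007) |
| Bootstrap-corrected CITL, mean (SD; largest absolute value) | 0.002 (0.009; 0.028) | -0.0005 (0.011; 0.031) |
| Cross-validated c-index | 0.495 | 0.771 |
| Cross-validated slope | -0.26 | 0.96 |
| CITL in new population, same baseline, mean (SD) | 0.002 (0.044) | -0.012 (0.053) |
| CITL in new population, baseline log-odds lower by 1.79 | -1.81 | -1.82 |

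Internal calibration-in-the-large does not separate the two models; the c-index and slope do. Only data outside the fitting sample move calibration-in-the-large.

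**Step 5, what a shift would look like.** The size is assumed; the documents give none. logit(0.60) = ln(0.6/0.4) = 0.405, logit(0.50) = 0 and logit(0.40) = -0.405. A fall from 60% to 50% is therefore about -0.41, and to 40% about -0.81. By the same arithmetic 30% gives -0.847 - 0.405 = -1.25 and 20% gives -1.386 - 0.405 = -1.79. These are approximate once predictors spread the risk.

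**The case against.** **A useless algorithm would get through.** A reader might infer this, and the documents do not support it. The four measures are read together, and discrimination is powered against an AUC of 0.75. A useless model shows a cross-validated c-index of about 0.50 and a slope far from 1. With no limit set for calibration-in-the-large, nothing formally passes or fails on it.

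**The value is zero by construction.** This too goes further than the plan allows. It is exact only on the fitted data. At N = 200 the useful model's cross-validated value reached 0.11. If predictions came from the mixed-model option using fixed effects only, the value would be -0.10, -0.25 or -0.37 for assumed random-intercept SDs of 1, 2 or 3. That departure comes from the model form and says nothing about transportability. Random folds are also my reading, since the unit is not stated and Section 9 refers to a SAP informed by a mid-study analysis.

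**A shift has been shown to exist.** It has not. PET and CSF results are quantified centrally (Sections 6 and 8.2), and inclusion criterion 11 requires central review. Updating referral on predictors already in a correctly specified model need not change risk given those predictors. The shifts above are inputs that the measure hands back.

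**Other analyses cover screen failures, and the aims are exploratory.** Aim 1 compares actual screen failure rates with other studies, and Aim 2 compares initial amyloid PET results with historical data. Both bear on screen failures, but neither tests the model's predictions. The exploratory label lowers the stakes without making an uninformative figure informative.

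These points limit the claim. They do not give the planned figure any content.

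**Conclusion.** The point holds in a limited form. With a maximum-likelihood logistic model, an intercept and ordinary random resampling, calibration-in-the-large is exactly 0 on the fitted data and at most about 0.03 after resampling at N = 2,000, whatever the model's quality. As planned it carries almost no information, and the plan has no other measure that would reveal a shift in baseline risk between sites or periods. Whether such a shift exists, and how large it is, cannot be told from the documents. This is a gap in the validation of one aim, inexpensive to close; it is no evidence that the algorithm is miscalibrated.

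**What to change.** In the SAP for Aim 2:

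1. Define the validation set as all participants tested for amyloid, positive and negative. The enrolled cohort alone will not do, because inclusion criterion 11 admits only elevated or intermediate amyloid.
2. Compute calibration-in-the-large and slope by leave-site-group-out (internal-external) cross-validation, with the grouping rule written down in advance.
3. Freeze the model at a stated date and compute both measures on participants tested later.
4. Report each hold-out and the spread across them. A single value pooled over left-out site groups would return towards 0 for the reason in Step 2.
5. State the unit of folds and resamples. Keep random 10-fold and bootstrap for optimism in the c-index and slope, and do not present calibration-in-the-large from them as evidence of calibration.

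This needs SAP wording and modest extra analysis of data the study already collects. The price is precision. With ten site groups of 200 (an assumed split), the standard error per group is roughly 1/sqrt(200 × 0.24) = 0.14, or ±0.28 at 95%. A later-period hold-out of 1,000 (also assumed) gives 1/sqrt(1000 × 0.24) = 0.065, or ±0.13. Both are somewhat larger when the predictors are strong. The figures may also be less favourable. If the hold-outs are not adopted, the SAP should say that transportability is not assessed.

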1.3 SCHEDULE OF ACTIVITIES (SOA)

The schedule below is for the In-Clinic TRC

Procedures	Screening (Stage 1-2 complete within 60-day window; Stage 3 complete within 84-day window)			Follow-up Visits ⁸ Every 6 months +/-21 days
	Stage 1	Stage 2 ³	Stage 3	
Informed consent	X			
Demographics	X			
Medical history	X			X
Concomitant Medication	X			X
Adverse events		X		X
Vital Signs ¹	X			X
Physical and Neurological exam	X			X
PACC	X			X
CFI	X*			X*
CDR-SB	X*			X*
STAI and GDS	X*			X*
Concerns about AD, Future Time Perspective Scale	X*		X ⁶	X*
Blood and urine for clinical labs	X			
Blood for Genomics ² and AD Biomarkers (fasted) ¹⁰	X			
Amyloid testing ³ by CSF ^{4,10} or PET		X		
Wellness Telephone Check ⁵		X	X	
Eligibility Discussion			X	
Impact of Events Scale			X ⁷	
Global Unique Identifier (GUID) generation	X ⁹			

¹Vital signs include weight, plus height at screening visit only.

²DNA collection performed for APOE Genotyping and banking/future analyses.

³Previous amyloid testing from external study may be used with approval from the Coordinating Center and screening stage 2 may be skipped.

⁴A coagulation panel and platelet count will be obtained either locally or centrally prior to the LP (within 3 months), in order to rule out a clotting disorder. Participants on anticoagulation are not eligible for LP.

⁵Post-LP/ post-PET, post-eligibility discussion telephone follow-up within 72 hours after procedure.

⁶Administered in-person after eligibility discussion.

⁷Administered by phone at the wellness telephone check following eligibility discussion.

⁸Screening visit procedures may be repeated at follow-up visits, with approval from the Coordinating Center, if needed to assess potential changes in eligibility for clinical trials, e.g. after participation in a clinical trial or prolonged enrollment in TRC without successful enrollment in a trial.

⁹GUID generation will occur at screening visit or at any visit thereafter once consent has been obtained

¹⁰CSF and Blood biomarker collection should occur after a minimum 8-hour fast

*At the discretion of the PI, these assessments may be conducted over the phone.

For those participants who are enrolled in the APT Webstudy, quarterly online participation will continue while screening for and enrolled in TRC.

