Analysis Plan: To assess the associations between web-based cognitive tests and in-person measures, linear mixed models will be used to accommodate the dependencies of scores over the follow-up time period. Such models accommodate different times of measurement, time varying and time invariant covariates as well as missed measurements and data from participants who are lost to follow-up. Permutation tests may be implemented to verify that valid p-values will be obtained even if model assumptions are not correct.

Power Analysis: Assuming a correlation coefficient of 0.6 as the true correlation between these measures, we have 90% power to observe a correlation as low as 0.67 with a sample size of 1000 participants and a type I error rate of 5%. Hence, the sample size will have adequate power to detect clinically meaningful associations between the web-based and in-person measures of decline.

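### The Aim 3 power figure is for one undefined correlation, not for the mixed-model analysis of decline it is said to support, and its 90% does not reproduce

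*Combined protocol and SAP*

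**What the plan says.** All of this is in the combined protocol and SAP, Section 9, Statistical Aim 3, unless another section is named.

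- **Hypothesis.** Web-based performance, functional measures and self- and study-partner report "will predict and subsequently track with in-person measures of cognitive (PACC) and functional (CDR-SB) decline".
- **Analysis.** "linear mixed models will be used to accommodate the dependencies of scores over the follow-up time period". No test against a correlation of 0.6 is described.
- **Power.** The starting point is "Assuming a correlation coefficient of 0.6 as the true correlation between these measures". From this the plan states that "we have 90% power to observe a correlation as low as 0.67". The sample is 1,000 participants and the type I error rate is 5%. Sidedness is not stated.
- **Conclusion drawn.** "the sample size will have adequate power to detect clinically meaningful associations between the web-based and in-person measures of decline".
- **Visit schedule (Section 1.3).** In-clinic follow-up is "Every 6 months +/-21 days". Web testing is quarterly for those enrolled in the APT Webstudy. Neither interval is used in the power paragraph.

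**The concern.** The hypothesis and the analysis concern change over repeated visits. The power paragraph concerns one correlation coefficient with no time point, change score or slope attached to it. The step from that coefficient to adequate power for decline is asserted, not derived.

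The gap matters in this design because the information on decline is uncertain:

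- Participants become inactive when they consent to a trial (Sections 5.4 and 7.1.1), and moving people into trials is the purpose of the cohort.
- Participants who develop dementia are discontinued (Section 7.1), which cuts off the follow-up of people who are declining.
- Direct referrals may bypass the Webstudy (Sections 2.3.1.4 and 8.1.1), so the number with paired web and clinic data is unknown.

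At stake is Aim 3's claim to validate web measures as trial outcomes. A reader would take from Section 9 that the design has been shown to be adequate for that claim.

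**Working it through.** **1. The plan's own figure.** Inputs from Section 9: 0.60, 0.67, N = 1,000, alpha 5%. One-sample Fisher z test, two-sided: power = Φ(|atanh r1 − atanh r0| × √(N − 3) − 1.960), with √997 = 31.575.

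- 0.60 versus 0.67: (0.8107 − 0.6931) × 31.575 = 3.713; 3.713 − 1.960 = 1.753; power **96.0%**. One-sided it is 98.1%. A simulation of the two-sided test gave 96.2%.
- 0.60 versus 0.53: (0.6931 − 0.5901) × 31.575 = 3.252; 3.252 − 1.960 = 1.292; power **90.2%**.
- 90% power for 0.60 versus 0.67 needs ((1.960 + 1.282)/0.1176)² + 3, about 763 participants.
- With N = 1,000 and 90% power, the detectable values are 0.662 upward and 0.530 downward.

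The stated 90% fits the downward alternative 0.53. The value 0.67 looks like its mirror image (0.60 + 0.07), but this is an inference. The wording also presents 0.67 as a low value although it lies above the correlation assumed to be true, so null and alternative are not clearly defined.

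**2. What the planned analysis depends on.** Power for an association of declines depends on the number and spacing of visits, length of follow-up, between-person slope variance, residual variance, attrition, and the number with paired data. None of these enters the power paragraph, and PACC and CDR-SB are not treated separately. The documents give no variances, attrition rate or paired count, so no single corrected power can be computed. The ranges below are assumptions.

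**3. Association of slopes tested against zero.** Assumed: true slope correlation 0.67; 1,000 people with complete paired data; 6-monthly clinic and quarterly web scores; the same ratio k (SD of true slope per year / residual SD) for both measures. Slope reliability = k²/(k² + 1/S), with S = Σ(t − mean t)². Over 1, 2, 3 and 5 years, S is 0.5, 2.5, 7.0 and 27.5 for clinic, and 0.625, 3.75, 11.375 and 48.125 for web. Observed r = 0.67 × √(clinic reliability × web reliability).

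Example, k = 0.3 at 2 years: clinic 0.09/(0.09 + 0.400) = 0.184; web 0.09/(0.09 + 0.267) = 0.252; observed r = 0.67 × √(0.184 × 0.252) = 0.144; power 99.6%.

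| k | 1 year | 2 years | 3 years | 5 years |
|---|---|---|---|---|
| 0.1 | 5% | 10% | 41% | >99% |
| 0.2 | 7% | 64% | >99% | >99% |
| 0.3 | 17% | 99.6% | >99% | >99% |
| 0.5 | 74% | >99% | >99% | >99% |

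These count rejection in either direction. Counting only the correct direction, the k = 0.1, 1-year value is about 3%. If reliability is simply set equal for both measures, 0.2 gives observed r = 0.134 and power 98.9%, and 0.3 or higher gives more than 99.9%.

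**4. Latent slopes, 0.60 versus 0.67.** This applies the plan's contrast to decline, correcting for reliability (rel) treated as known: r_obs = rel × r; SE ≈ (1 − r_obs²)/(rel × √1000); power = Φ((0.07 − 1.96 × SE0)/SE1).

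Example, rel = 0.9: r_obs = 0.540 and 0.603; SE0 = 0.0249; SE1 = 0.0224; (0.07 − 0.0488)/0.0224 = 0.95; power 83%.

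| Reliability | 1.0 | 0.9 | 0.8 | 0.7 | 0.5 | 0.3 |
|---|---|---|---|---|---|---|
| Power | 96% | 83% | 64% | 47% | 22% | 10% |

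Under the step 3 schedule with k = 0.3, the same contrast has about 7% power at 2 years, 18% at 3 years and 57% at 5 years. Treating reliability as known makes all of these optimistic.

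**The case against.** The sponsor has a fair reply. Under Aim 1, Section 9 says the sample size was set by the need for a cohort large enough to support an efficacy trial, not by power. The aims are called exploratory, and point estimates with confidence intervals are already required. Analysis detail is deferred to a SAP informed by a mid-way look. No enrolment rule or decision hangs on this sentence. All of that stands and limits the consequence. It does not make the conclusion about decline follow from the calculation.

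Three stronger readings are tempting, and the documents do not support them.

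- **That Aim 3 is underpowered.** The low figures in step 4 belong to a test against 0.60, which the analysis plan does not contain. Detecting an association is more naturally a test against zero, and there power is high over most of the assumed range. Short follow-up cannot be taken as given either: Section 1.1 gives a participant duration of 5 years, and Section 5.4 returns people to active status after a trial.
- **That 0.6 is a cross-sectional, error-free correlation.** The text attaches no time point and no reliability to it. It could be a correlation of changes or slopes, or an observed value already reduced by measurement error. What can be said is that it is undefined.
- **That unreliability pushes the slope correlation below the 0.60 null.** This compares an attenuated correlation with an unattenuated reference value. A joint model that estimates the latent slope correlation reduces that bias, at a cost in precision.

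**Conclusion.** The concern holds as a missing basis, not as a demonstrated shortfall. The stated power belongs to a test of one undefined correlation and is not a property of the planned mixed-model analysis, so the claim of adequate power for decline is unsupported.

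Whether power is in fact adequate depends on quantities the documents do not give. Under the assumptions shown, a test against zero is weak only when slope variance is small and follow-up short (5% to 41% over 1 to 3 years at k = 0.1; 17% at 1 year for k = 0.3). A 0.60 versus 0.67 contrast of latent slopes drops below 90% with modest unreliability. Fewer than 1,000 paired participants would lower power in both cases.

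Separately, and without any outside assumption beyond the standard Fisher z test, the 90% is not what 0.60, 0.67 and N = 1,000 give: the result is 96.0% two-sided.

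**What to change.** 1. State what the correlation is (which measures, at what time, scores or change), its null and alternative, and whether the test is one- or two-sided. Correct or explain the pairing of 90% with 0.67. Relabelling it as a baseline correlation is not enough, since that gives 0.6 a meaning the documents do not state and leaves the 90% wrong.
2. Remove the reference to decline from the power conclusion unless a calculation supports it.
3. Specify the decline estimands, separately for PACC and CDR-SB, each with a 95% confidence interval. For tracking, one option is the slope-slope correlation from a bivariate linear mixed model. For prediction, one option is the effect of baseline or early web change on later in-person change.
4. Obtain power or precision for these estimands by simulating the planned models. Take variance components, follow-up including trial-related inactivity, attrition and the paired count from the mid-way look that Section 9 already plans.

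The cost is SAP wording and a short simulation. No new data are needed. The stated power may become less favourable.
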